5.1. Summary of Study Design

Study I7S-MC-HBEH (HBEH) is a multicenter, randomized, double-blind, parallel-group, placebo-controlled, fixed-dosage, Phase 2a study comparing 3 dosages of LY3154207 (10, 30, or 75 mg administered orally once a day [QD]) with placebo over 12 weeks in subjects with mild-to-moderate dementia associated with Lewy body dementia (LBD) (Parkinson’s disease dementia [PDD] and dementia with Lewy bodies [DLB]). The study includes a Screening Period (Visits 1 to 2) of a minimum of 7 days and up to 14 days, a 14-day Pretreatment Period (Visits 2 to 3), a 12-week Treatment Period (Visits 3 to 11), and a 14-day Safety Follow-Up Period (Visits 11 to 801) (Figure HBEH.5.1). Subjects who meet entry criteria will be randomized in a 1:1:1:1 ratio to LY3154207 (10 or 30 or 75 mg QD) or placebo. The primary objective of this study is to test the hypothesis that LY3154207 administration for 12 weeks will result in a significant improvement in cognition as measured by the change from baseline to Week 12 in the Continuity of Attention (CoA) composite score of the Cognitive Drug Research Computerized Cognition Battery (CDR-CCB), in subjects with mild-to-moderate LBD, compared to placebo. The CoA has demonstrated a significant treatment effect in previous trials in subjects with PDD and is resistant to learning and placebo effects (Wesnes et al. 2005; Rowan et al. 2007).

[figure not shown]

Figure HBEH.5.1. Illustration of study design for Clinical Protocol I7S-MC-HBEH.

5.2. Determination of Sample Size

Approximately 750 subjects will be screened to achieve 340 randomized subjects. The randomization will be 1:1:1:1 to LY3154207 (10, 30, or 75 mg QD) or placebo treatment arms.

CCI

If the true effect size for LY3154207 relative to placebo on the CoA is 0.4 with the sample size of 340, there will be greater than 80% probability of passing this criterion. A 20% discontinuation rate by Week 12 has been accounted for in the sample size determination.

Sample size estimation was based on an article by Wesnes et al. (2005) where the difference in mean change from baseline for rivastigmine compared to placebo and the pooled standard deviation (SD) for CoA were estimated as 5.7 units and 18 units, respectively. The rivastigmine effect corresponded to a reduction in the deficit of subjects compared to age-matched healthy volunteers of approximately 45%. Based on this result, the effect size of 0.4 in this study corresponds to a mean difference of 7.2 units (approximately 57% reduction in the deficit).

This sample size will allow assessment of the in-clinic blood pressure (BP) and pulse rate (PR) values on the first day of dosing in order to evaluate any changes after the first dose of treatment that was seen in Phase 1. If the SD of the in-clinic systolic blood pressure (SBP) value is assumed to be 15 mm Hg, then the difference from the mean to the upper limit of a 95% confidence interval (CI) of the change from baseline in SBP relative to placebo is expected to be <4.7 mm Hg. If there is any initial rise in BP or PR, the in-clinic 6- and 12-week assessments along with the home blood pressure monitoring (HBPM) and ambulatory blood pressure monitoring (ABPM) measures will be used to assess whether the rise accommodates. The difference from the mean to the upper limit of a 95% CI in the change in average SBP measured at each of these visits relative to placebo is expected to be <3.5 mm Hg. This assumes an SD of 10 mm Hg and a 20% discontinuation rate.

Simulations were conducted in FACTs Version 5.1.1 using a Bayesian normal dynamic linear model (NDLM).

5.3. Method of Assignment to Treatment

Subjects who meet all criteria for enrollment will be randomized to double-blind treatment at Visit 3. Subjects will be randomized in a blinded fashion to the 4 treatment arms (LY3154207 10, 30, or 75 mg QD or placebo) in a 1:1:1:1 ratio. Randomization will use a minimization procedure in order to balance for investigator site and the current use of acetylcholinesterase inhibitors (AChEIs) (Yes, No) using an interactive web-response system (IWRS).

The IWRS will be used to assign blister packs containing double-blind investigational product to each subject. One blister pack will be dispensed for each week of dosing (for example, for 14-day study intervals, 2 blister packs will be dispensed at each visit). Site personnel will confirm that they have located the correct blister packs by entering a confirmation number found on the blister packs into the IWRS.

6. A Priori Statistical Methods

6.1. Populations for Analyses

For purposes of analyses, the following populations are defined:

Population	Description
Enrolled	All subjects who sign informed consent.
Evaluable Patient population (EPP)	All randomized subjects who received at least 1 dose of study medication, who have the baseline efficacy assessment, and have at least 1 post-dose efficacy assessment. Analyses will be according to the treatment the subject actually received.
Completers	All randomized subjects who have completed all study procedures including follow-up and/or early termination/discontinuation visit.
Safety population	All randomized subjects who take at least 1 dose of double-blind study treatment. In the event of a treatment error, subjects will be analyzed according to the treatment they actually received.
Per Protocol population	Subjects who complete the study with no major protocol deviations.
PK Analysis population	PK analyses will be conducted on subjects who receive at least 1 dose of the study drug and have 1 measurable concentration.

Abbreviations: PK = pharmacokinetic.

6.2. General Considerations

Statistical analysis for this study will be the responsibility of Eli Lilly Company (Lilly) or its designee. The statistical analyses performed as part of the interim analyses will be conducted by the designated statistical analysis center, which forms part of the internal assessment committee (IAC) (see Unblinding and Communication Plan for more details).

Analyses will be conducted in SAS Version 9.4 or greater, and Spotfire graphical package will be used to review safety data on an ongoing basis during the trial (for example, for trial level safety reviews). Packages to be used for the analysis of digital biomarker data will be specified in the Digital Biomarker Analysis Plan.

As HBEH is a Phase 2 study, the appropriate estimand is a de jure estimand, where efficacy of LY3154207 is assessed under the paradigm of all subjects taking study drug as intended. Intercurrent events for HBEH are defined to be when subjects discontinue the study prior to completing the 12 weeks of treatment. While subjects are allowed to be on steady doses of symptomatic treatments, the protocol does not allow for subjects to initiate any therapeutic agent that has been demonstrated to be effective for treatment of cognition in LBD during the trial. The primary analyses use a Bayesian mixed-model repeated measures (MMRM) analyses of the CDR-COA to evaluate cognition in subjects with mild-to-moderate LBD compared with placebo. This analysis assumes that the intercurrent events lead to data that is missing at random (MAR).

Unless otherwise specified, all efficacy analyses will be conducted on the Evaluable Patient population (EPP). Analyses will be conducted according to the treatment the subject actually received.

When change from baseline is assessed, subjects will be included in the analysis only if both the baseline and a postbaseline measure are available. Unless otherwise defined, a baseline measure is the last non-missing observation collected prior to the subject receiving study treatment.

Safety analyses will be conducted on the safety analysis set comprising all subjects who received at least 1 dose of study medication. Summary statistics, tabulations, and graphs will be provided as appropriate.

Longitudinal analyses from baseline to Week 12 will use the change from baseline score as the response variable. An unstructured covariance matrix will be considered for MMRM; however, if this fails to converge, other structures will be considered based on the trial design. Unless stated otherwise, for all MMRM analyses, the difference in least squares (LS) means between LY3154207 and placebo, corresponding 95% credible or CIs, and p-values will be presented.

Any change to the data analysis methods described in the protocol will require an amendment ONLY if it changes a principal feature of the protocol. Any other change to the data analysis methods described in the protocol, and the justification for making the change, will be described in the clinical study report (CSR).

Only key analyses and results relating to primary and secondary objectives will be presented in the CSR. Exploratory and sensitivity analyses are not expected to be included in the CSR, unless they are relevant to the trial conclusions. Further exploratory analyses, in addition to those specified in this SAP may be conducted, if deemed appropriate.

6.3. Adjustments for Covariates

Unless stated otherwise, the following covariates will be included in efficacy analyses: baseline, baseline by visit interaction, age, and concomitant use of AChEIs at baseline.

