10.3.3.2. Secondary Efficacy Analyses

The secondary efficacy outcomes (ADCS-CGIC, PDAQ-15, ADAS-Cog₁₃, CDR-CCB PoA, D-KEFS, MoCA, NPI, ESS, and MDS-UPDRS [total and Part III]) will be assessed at the 12-week time point. Each of these secondary endpoints will be analyzed using an MMRM model, which will include terms for: baseline value, treatment, visit, and the relevant interaction terms. Further covariates may be included such as age, site, and the severity of PD motor function as well as severity of dementia at baseline as appropriate. The change of the score from baseline will be the dependent variable. If subscores for a particular scale are deemed clinically relevant to analysis, it will be completed as an exploratory analysis.

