6.12. Efficacy Analyses

6.12.1. Primary Outcome and Methodology

The primary objective is to evaluate whether LY3154207, administered at 10 mg, 30 mg, and/or 75 mg QD oral dosing for 12 weeks, will show an improvement in cognition compared to placebo in subjects with mild-to-moderate LBD. This objective will be assessed in the EPP using a Bayesian MMRM analysis of the change in the CDR-CCB CoA data from baseline to Week 12. Continuity of Attention (CoA) is defined as the sum of correct responses from the Choice Reaction Time and Digit Vigilance Task with the number of Digit Vigilance Errors subtracted.

The primary analysis on CoA will occur when all subjects have had the opportunity to complete 12 weeks of treatment.

The analysis of CoA will utilize a Bayesian MMRM model. The Bayesian analysis will use uninformative priors for all terms in the model. For the model coefficients, these will be diffuse Normal distributions centered on zero. Prior for covariance matrix will follow an inverse-Wishart distribution (the multivariate generalization of an inverse gamma distribution for a variance component). The MMRM model will account for longitudinal data assessed throughout the study after 1, 2, 4, 6, 8, 10, and 12 weeks of dosing. The change in CoA from baseline to Week 12 will be the dependent variable. The model will comprise fixed (baseline value, treatment, visit, age, and use of AChEIs) with the interaction terms (treatment by visit, baseline value by visit) with repeated measures of visit within subject. Visit will be considered a categorical variable with values equal to the visit numbers at which the CoA was assessed. Covariates may be centered prior to analysis to aid model convergence.

The primary comparison will be the contrast between treatments and placebo for the Week 12 change from baseline against a null hypothesis of no difference. This will be presented as both a difference in estimated means of the 12-week change and the effect sizes over the 12 weeks. The average effect size from the last 4 visit time points (Weeks 6, 8, 10, and 12) will be the primary comparison between treatments and placebo. These will be averaged after the model has been fit.

Example codes, for the purposes of aiding programming of the primary analysis, using Bayesian MMRM and equivalent frequentist MMRM, are given below.

Bayesian MMRM Model:

```
Proc MCMC data=coa_final nbi=2000 ntu=50 nmc=10000 seed=2019143 thin=10 diag=all

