6.12.3. Secondary Efficacy Analyses

The secondary efficacy outcomes (PDAQ-15, ADAS-Cog₁₃, CDR-CCB PoA, D-KEFS, MoCA, NPI, ESS, and MDS-UPDRS) will be assessed at the 12-week time point as the primary analysis. Each of these secondary endpoints will be analyzed using a frequentist MMRM model, which will include terms for: baseline value, treatment, visit, age, concomitant use of AChEIs, and the relevant interaction terms (treatment by visit, baseline by visit). The change in score from baseline will be the dependent variable. If subscores for a particular scale are deemed clinically relevant to analysis, it will be completed as an exploratory analysis.

For the Alzheimer’s Disease Cooperative Study – Clinician Global Impression of Change (ADCS-CGIC), a logistic regression analysis will be performed with treatment, visit, age, concomitant medication of AChEIs, and relevant interaction terms. Two different endpoints will be assessed: “moderately or better,” defined as subjects who had moderate/marked improvement and “minimally or better” defined as subjects who had minimal/moderate/marked improvement on the ADCS-CGIC scale.

Levodopa equivalency dose (LED) will be calculated using the conversion factors (Tomlinson et al. 2010) of the actual daily dose (mg) of the relevant PD drugs (Table HBEH.6.1). After the LED is calculated for each concomitant medication that a subject is taking, the total LED will be used as a covariate for the analyses of the MDS-UPDRS scales. The impact of LED may be explored for various efficacy and safety measures.

Table HBEH.6.1. LED Conversion Factors

Medication	Multiplication Factor
Immediate release L-dopa dose	1
Controlled release L-dopa dose	0.75
*Entacapone	LD × 0.33
*Tolcapone	LD × 0.5
Duodopa	1.11
Pramipexole (as salt)	100
Ropinirole	20
Rotigotine	30
Selegiline – oral	10
Selegiline – sublingual	80
Rasagiline	100
Amantadine	1
Apomorphine	10

Abbreviation: LED = levodopa equivalency dose.

Note: *LD represents immediate release L-dopa dose for particular patient.

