6.14.7. Additional Safety Sections

6.14.7.1. Secondary Safety Analyses: In-Clinic Blood Pressure/Pulse Rate

- Day 1 (Visit 3) In-clinic BP and PR change post first dose

Change in in-clinic BP and PR from 0 up to 8 hours post dose measured on the first day of study drug dosing will be analyzed using an MMRM analysis with baseline value, treatment, time post dose (hours) as fixed effects, and treatment by time and baseline by time as interaction terms with repeated measures of time (hour) within subject. Two baselines will be considered: the Visit 3 pretreatment value (Time 0) and the time-matched baseline values from Visit 2 (hourly value 0-6 hours). For the second of these, there is no time-matched value for the Visit 3 7- and 8-hour time points, so these will use the Visit 2 6-hour time point as their baseline value. A separate change from baseline analysis will be completed for each baseline approach.

- Change in in-clinic BP and PR from baseline (Visit 2, predose) up to Week 12 (Visit 11)

To assess the impact of LY3154207 on BP and PR over time, change from baseline in in-clinic BP and PR to Week 12 will be analyzed using MMRM with response variable being the daily average of 0 to 6 hours, with fixed effects for baseline value, treatment, visit, and treatment by visit and baseline by visit as interaction terms with repeated measures of visit within subject. Change from baseline in BP and PR will be assessed at both 6 and 12 weeks. Analysis at 6 weeks will help to evaluate any significant changes (if any) in BP and PR earlier than 12 weeks (end of study) and if they accommodate by 6 weeks.

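### The ADCS-CGIC logistic model has no baseline severity covariate, and the BP and pulse models omit AChEI use, a minimisation factor; both cost a little precision

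*SAP*

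**What the plan says.** SAP 6.3 allows for exceptions stated elsewhere and otherwise lays down that "the following covariates will be included in efficacy analyses: baseline, baseline by visit interaction, age, and concomitant use of AChEIs at baseline". It is a default for efficacy, open to exceptions. The primary CoA model in SAP 6.12.1 follows it: "The model will comprise fixed (baseline value, treatment, visit, age, and use of AChEIs", plus the two interactions with visit.

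For ADCS-CGIC, SAP 6.12.3 replaces the MMRM with two responder endpoints: "a logistic regression analysis will be performed with treatment, visit, age, concomitant medication of AChEIs, and relevant interaction terms". There is no baseline or severity term. Protocol 9.1.2.1.1 describes ADCS-CGIC as a 7-point rating of change, anchored by a baseline interview but without a baseline score.

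For secondary endpoints, Protocol 10.3.3.2 allows optional further covariates, including "the severity of PD motor function as well as severity of dementia at baseline as appropriate".

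For safety, the Week 6 and Week 12 in-clinic BP and pulse MMRM in SAP 6.14.7.1 is specified "with fixed effects for baseline value, treatment, visit, and treatment by visit and baseline by visit as interaction terms". The Day 1 model there and the home BP model in SAP 6.14.7.3 have the same structure, with hour or day in place of visit. None contains AChEI use or age. SAP 5.3 says that minimisation is used to "balance for investigator site and the current use of acetylcholinesterase inhibitors (AChEIs) (Yes, No"). Site is left out of every model, with reasons given in SAP 6.6.

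**The concern.** A model for a change rating loses the covariate that usually does the most work. Every secondary MMRM carries the subject's starting score; the ADCS-CGIC model carries nothing that measures how impaired the subject was at entry. The sponsor regards severity as relevant to this endpoint, because SAP 6.15 offers MoCA bands of 10-16 and 17-23 as a subgroup for it. MoCA is scored at Visit 1 and is an entry criterion, so using it would lose no subject. In a logistic model, leaving out a prognostic covariate lowers power and pulls the treatment odds ratio towards 1 relative to the severity-conditional value.

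For BP and pulse, balancing allocation on a factor and then ignoring it leaves any variance it explains in the residual. The standard error is then slightly larger than the design warrants. Precision of the SBP comparison is a stated purpose of the sample size (Protocol 10.1, SAP 5.2).

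**Working it through.** **BP precision: the plan's own figures first.** SAP 5.2 gives SD 15 mm Hg for Day 1, and SD 10 mm Hg with 20% discontinuation for Weeks 6 and 12. With 340/4 = 85 per arm, 0.8 × 85 = 68 remain. The 95% half-width is 1.96 × SD × √(2/n).

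- Day 1: 1.96 × 15 × √(2/85) = 4.51 mm Hg (plan: below 4.7).
- Weeks 6 and 12: 1.96 × 10 × √(2/68) = 3.36 mm Hg (plan: below 3.5).

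Both reproduce.

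**Effect of adding AChEI use and age.** If they explain a fraction R² of the residual variance, the standard error is multiplied by √(1 − R²). The documents give no R²; 1 to 4% is assumed.

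| R² (assumed) | SE reduction | Day 1 half-width | Week 6/12 half-width |
|---|---|---|---|
| 0 | 0 | 4.51 | 3.36 |
| 1% | 1 − √0.99 = 0.5% | 4.49 | 3.35 |
| 4% | 1 − √0.96 = 2.0% | 4.42 | 3.29 |

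The gain is about 0.02 to 0.09 mm Hg on Day 1 and 0.02 to 0.07 mm Hg later.

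**ADCS-CGIC.** The plan states no power for this endpoint, so there is no figure to reproduce. The check simulates one active arm against placebo at one time point, with 68 per arm and 1,500 runs per setting. Two-sided p below 0.05 counts as success. The placebo response is assumed to be 30% and the conditional odds ratio 2.33 (log 0.846). Severity is a standard normal covariate with an assumed log odds ratio per SD. Each data set is fitted with and without severity; age, AChEI use and repeated visits are not modelled.

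| Severity log-OR per SD | Power without | Power with | Gain (points) | Mean treatment log-OR without / with | Type I error without / with |
|---|---|---|---|---|---|
| 0 | 65.3% | 65.8% | 0.5 | 0.856 / 0.863 | 4.3% / 4.5% |
| 0.3 | 64.7% | 66.0% | 1.3 | 0.846 / 0.869 | 3.9% / 4.3% |
| 0.6 | 58.1% | 62.5% | 4.4 | 0.794 / 0.868 | 4.4% / 4.6% |
| 1.0 | 50.0% | 58.9% | 8.9 | 0.725 / 0.885 | 4.8% / 5.3% |

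The Monte Carlo standard error of a single power estimate is about √(0.6 × 0.4/1500) = 1.3 points. It is smaller for the gains, because both models are fitted to the same data. The 1.3-point gain at 0.3 should be read as small rather than exact.

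The lower log odds ratio without severity reflects non-collapsibility: the unadjusted model targets a different, less conditional quantity. It is not bias, and type I error stays at about 4 to 5% in both models.

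**The case against.** A reader might infer from SAP 6.3 that covariates are strictly limited and that baseline dementia severity goes unused. The documents do not support that. The section is a default, and SAP 6.12.3 adds total levodopa-equivalent dose for the MDS-UPDRS scales. The CoA, PoA, ADAS-Cog13 and MoCA models each adjust for their own baseline, which is itself a measure of cognitive impairment. Severity is tabulated by arm (SAP 6.9) and offered as a subgroup (SAP 6.15). Nor is there a conflict with the protocol, since the severity covariates in Protocol 10.3.3.2 are optional.

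A reader might also want MoCA and diagnosis in every efficacy model. For the MoCA endpoint this fails: screening MoCA is already the baseline, and a second copy is exactly collinear. For CoA the case is weak, because Visit 2 CoA already carries most of the information. PDD versus DLB is a soft label here: Protocol 5.1.1.1.4 allows a PD classification whatever the timing of dementia, and Protocol 5.4 treats the two as one disease apart from that timing.

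The remaining objections concern size. The baseline interview already ties each ADCS-CGIC rating to the subject's own starting state, so severity may predict change only weakly. The severity effects are assumed, the BP gain is below 0.1 mm Hg, and the omission errs on the conservative side. All of this stands, and it makes the point a minor one. It does not explain why the one efficacy model without an own-baseline term has no substitute, or why a minimisation factor included for efficacy is left out for BP without a stated reason.

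**Conclusion.** The point holds for two sets of models and is modest in both.

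- **ADCS-CGIC:** there is no baseline severity covariate, although one is available for every subject. The cost is roughly 1 to 5 points of power for severity log odds ratios of 0.3 to 0.6 per SD, and about 9 at 1.0. This rests on an assumed 30% placebo response, an assumed conditional odds ratio of 2.33, and a simplified two-arm, single-visit model.
- **In-clinic and home BP and pulse:** AChEI use is omitted, and age with it. Intervals are, if anything, slightly too wide: adjustment would reduce standard errors by 0.5 to 2.0% if the two covariates explain 1 to 4% of residual variance, and by nothing if they explain none.

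A reader might go further and infer biased treatment comparisons or an inflated false-positive rate. Neither follows: randomisation protects the comparison, simulated type I error was near nominal with or without severity, and omitting a balancing factor is conservative. Leaving site out as well is a reasoned choice in SAP 6.6 and forms no part of this point.

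**What to change.** In SAP 6.12.3, add screening MoCA as a continuous covariate to the ADCS-CGIC logistic model. In SAP 6.14.7.1 and 6.14.7.3, add baseline AChEI use and age to the BP and pulse MMRMs. Alternatively, state why they are left out. Do not add MoCA to the MoCA endpoint model. MoCA or PDD/DLB diagnosis in the CoA model is optional.

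SAP 3 (Revision History) records that Version 3 was approved after unblinding. In this trial, therefore, keep the prespecified models as the planned analyses and report the adjusted ones beside them as labelled sensitivity analyses. In a later trial they could be prespecified as the main models.

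The cost is a few lines of SAP text, one extra coefficient in the ADCS-CGIC model and two in each BP or pulse model, with no new data. The one real downside is interpretive: the ADCS-CGIC odds ratio becomes conditional on severity and will not be directly comparable with the unadjusted one, which needs a sentence in the report.
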